2 INTRODUCTION

2.1 STUDY RATIONALE

Having reliable access to hearing health care services in the United States does not equate that individuals with hearing impairment will purchase and use hearing aids. Today, an estimated 3.4 million people in the US experience hearing study difficulties, have an objectively measurable hearing loss, but still do not use any device to mitigate their hearing loss problem. There are many reasons that an individual does not pursue adopting a hearing healthcare solution. Accessibility and affordability are two of the main reasons reported in the latest MarkeTrak 10 survey (Edwards, 2020). The stigma associated with hearing aids, lack of awareness or lack of confidence that hearing aids would help are other reasons.

Self-fitting (SF) hearing aids address primarily the accessibility and affordability issues. These SF hearing aids may expand the reach of hearing health care by meeting the unmet needs of a segment of people with hearing loss who, until now, have rejected traditional hearing aids.

The Sponsor is conducting this NSR device study to fulfill one of the special controls, 21 CFR § 874.3325(b)(1) *Clinical data must evaluate the effectiveness of the self-fitting strategy...* for self-fitting air conduction hearing aids. The primary purpose of the SF Study is to validate the effectiveness of the *Vibe SF* strategy based on the device's intended use and technological characteristics. The SF Study final clinical study report will be part of the 510(k) submission for the *Vibe SF* hearing aid.

2.2 BACKGROUND

The Original Hearing Aid Act in 1977 led the FDA to designate hearing aids as medical devices. Hearing Aids were listed under the Food and Drug Administration Modernization Act of 1997 (FDAMA) or the 21st Century Cures Act of 2016 as exempt from premarket notification requirements. In October 2018, the FDA established the new Class II device type, self-fitting air conduction hearing aid (21 CFR § 874.3325) with special controls.

SF strategy clinical data are described by Sabin et al. (2020) who conducted a similar validation investigation on the predicate device, the self-fitting and direct-to-consumer (DTC) BOSE® Hearing Aid (DEN180026, 2018).

The Sponsor believes that a 510(k) clearance of this SF device supports its positioning to fulfill the upcoming FDA proposed rule on Over-the-Counter (OTC) hearing aids as required in the 2017 Over-the-Counter (OTC) Hearing Aid Act.

2.3 RISK/BENEFIT ASSESSMENT

2.3.1 KNOWN POTENTIAL RISKS

The risk management process for the self-fitting hearing aid system is performed in accordance with the requirements stated in ISO 14971:2007, and the risk analysis results are used to identify and implement appropriate product development activities. The risk analysis in the Risk Management File for the self-fitting hearing aid system conducted by SPONSOR includes the identified risks in 21 C.F.R. § 874.3325 and in the validation investigation on the predicate device, the self-fitting and direct-to-consumer (DTC) BOSE® Hearing Aid (see Appendix 1).

Table 1 below lists the identified risks related to the self-fitting system of the *Vibe SF* hearing aid and *EasyFit* web application (*EasyFit*).

Mitigations to prevent over-amplifications include a safety output limiter which is a hardware measure for limiting the output sound pressure level (OSPL) in failure mode. Hence, for the implemented cluster, the safety limiter is 6 dB above maximum OSPL of the specific cluster. Other mitigation measures include performance testing as electroacoustics and software verification and validation. Critical use-related scenarios (critical tasks) and essential functions have been identified and will be tested and validated in Human Factors testing.

Table 1. Overview of identified risks related to self-fitting system clinical study

Identified Risk	Mitigation Measures	Support
Diminished hearing due to over-amplification caused by: • Excessively high sound output levels in the ear canal	• Software verification and validation (performance testing) • Electroacoustic (performance testing) • Safety Limiter implemented in design • Maximum possible output 114 dB • Screening of subjects to confirm mild-to-moderate hearing loss	• ANSI S3.22 electroacoustic testing
Diminished hearing due to over-amplification caused by: • Confusing and switching left and right hearing aid	• Safety Limiter implemented in design Labeling • IFU and Workflow show Left/Right Hearing Aid (Labeling) • L/R mark on the device to distinguish between left and right hearing aid	• Software verification and validation (performance testing) • Design verification
Listening fatigue or failure to provide sound awareness due to over- or under-amplification caused by: • Poor fitting • Use error • Confusion L/R	• Software verification and validation (performance testing) • Electroacoustic (performance testing) • Safety Limiter implemented in design Labeling • IFU and Workflow show Left/Right hearing aid (Labeling) • L/R mark on the device to distinguish between left and right hearing aid	• Software verification and validation (performance testing) • Human factors validation • Pilot Study

Identified Risk	Mitigation Measures	Support
Diminished hearing due to unintended use as hearing protection in loud environments.	
Labeling
 
 Do not use this device as hearing protection in loud environments. Frequent exposure to loud sounds may harm your hearing. Keep the loudness at comfortable listening levels. Wear hearing protection when exposed to loud environmental noise. 	
 Human factors validation

 Wrongly treated hearing loss Unintended user (severe hearing loss) selects the SF hearing aid despite having a severe hearing loss. Severe hearing loss remains untreated and worsens. 	
 Labeling Web application has built in measures if the response is outside the fitting range. Screening confirms that subjects have mild-to-moderate hearing loss 	
 Human factors validation Software verification and validation (performance testing)

Diminished hearing due to over-amplification caused by:
 
 Hearing ability profiling: Intended user does not count how many tones he / she hears leading to wrong clusters selected. 	
 Built-in measures in the web application to check consistency in the answers of the users on how many tones heard. Comfort loudness adjustable by the user after the hearing ability profiling. 
Labeling
 
 Perform the hearing ability profiling in a quiet environment without interruptions for the best result. 	
 Human factors validation Software verification and validation (performance testing)
Acoustic Smartphone App can provide a high sound pressure level (SPL) / output to the patient's ear causing discomfort in the ear.	
The tones are extremely short and not perceived by most people
 
These types of remote controls have been marketed for many years and proven to be reliable and safe
 
Labeling
 
 The smartphone generates short tone sequences to control the hearing aids. Do not hold the smartphone close to the ear while using the app. 	
 Human factors validation

2.3.2 KNOWN POTENTIAL BENEFITS

Hearing aids relieve the strain of hearing, i.e., less strain and more clear hearing. It is anticipated that inexperienced wearers will experience improved ease and better speech understanding in various listening environments, e.g., watching television, conversations.

Subjects get the chance to try out state-of-the-art modern hearing aids. Inexperienced hearing aid subjects gain experience with hearing aids which will help them to make an informed choice if they decide to

purchase hearing aids upon conclusion of the study. Subjects already fitted with hearing aids will gain experience with SF hearing aids as well as the instant-fit completely-in-canal (CIC) form factor.

During screening the hearing of the subjects is checked by HCP thus the subjects gain current information about the status of their hearing.

Having to fill out the EMA surveys daily may have the benefit that subjects pay more attention to their hearing which might lead to increased perceptiveness of sound being an incentive to become more socially active. Overall, this could contribute to their emotional well-being.

2.3.3 ASSESSMENT OF POTENTIAL RISKS AND BENEFITS

Overall, all risks identified are mitigated as low as possible / below the risk acceptability threshold. The risks associated with the use of the *Vibe SF* hearing aid system are acceptable when weighted against the expected benefits to the study subjects. The benefit outweighs the overall residual risk.

In conclusion, the overall residual risk and the overall risk/benefit profile is acceptable for the clinical study using the self-fitting system *EasyFit* web application and *Vibe SF* hearing aid.

3 OBJECTIVES AND ENDPOINTS

OBJECTIVES	ENDPOINTS	JUSTIFICATION FOR ENDPOINTS
Primary		
Primary Effectiveness	
To demonstrate that the Vibe SF strategy is non-inferior to the HCP fit strategy in subject's perceived hearing aid benefit after wearing the Vibe SF and Silk 1X HCP fit hearing aids in real-life conditions.
 
Differences in the benefit scores on each of the three communication subscales as captured by the Abbreviated Profile of Hearing Aid Benefit (APHAB) after wearing each Vibe SF/ Silk 1X HCP fit hearing aids for 14 days.
 
The three communication subscales on the APHAB are: ease of communication (EC), background noise (BN) and reverberant room (RV). There is one benefit score (i.e., = unaided - aided) for each communication subscale (EC, BN and RV) scored after each fitting strategy field testing (SF or HCP fit): $\Delta EC(benefit)_{SF}$, $\Delta BN(benefit)_{SF}$, $\Delta RV(benefit)_{SF}$ for the Vibe SF hearing aids, and $\Delta EC(benefit)_{HCP\ fit}$, $\Delta BN(benefit)_{HCP\ fit}$, $\Delta RV(benefit)_{HCP\ fit}$ for the Silk 1X HCP fit hearing aids.
	
Self-reporting questionnaires have been commonly used to measure subjective hearing impairment.
 
The APHAB is selected because of its known psychometric properties. The APHAB was specifically designed to quantify auditory disability so that the success of the hearing aid fitting in reducing disability and comparison between hearing aid fitting strategies may be examined (Cox & Alexander, 1995).
 
The reason to examine each subscale independently is to investigate whether the fitting strategies provide different benefit in varying kinds of environments in the real world.

OBJECTIVES	ENDPOINTS	JUSTIFICATION FOR ENDPOINTS
	
For each subject, the endpoints are the 3 communication subscale differences between the HCP fit subscale (benefit) score and corresponding SF subscale (benefit) score:
 
 • $\Delta EC(\text{benefit})_{\text{HCP fit}} - \Delta EC(\text{benefit})_{\text{SF}}$ • $\Delta BN(\text{benefit})_{\text{HCP fit}} - \Delta BN(\text{benefit})_{\text{SF}}$ • $\Delta RV(\text{benefit})_{\text{HCP fit}} - \Delta RV(\text{benefit})_{\text{SF}}$ 
Time point data collected: Cross-over Design: Visit 1, 2, 3
 
Parallel-arm Design: 12 subjects: Visit 1, 2, 3 38 subjects: Visit 1 and 2
	
Secondary		
Secondary Hearing Aid Benefit:		
To score each of the following performance measures when the subject is using the Vibe SF and Silk 1X HCP fit hearing aids:		
1. Sound quality, speech understanding and hearing aid satisfaction real-time assessment	
The subject's sound quality, speech understanding and hearing aid satisfaction Ecological Momentary Assessment (EMA) scores measured repeatedly under real-life conditions.
 
Time point data collected: Cross-over Design: Field Test 1 and Field Test 2
 
Parallel-arm Design: 12 subjects = Field Test 1 and 2 38 subjects = Field Test 1
	
Assessment of perceived hearing aid benefit should include the dimension perceived sound quality, speech understanding and hearing aid satisfaction.
 
Only a couple of studies have allowed users to make multiple adjustments or sound quality judgments under real-life conditions. We want to further the research on standardizing the sound quality and speech understanding satisfaction assessment questions asked in real-life conditions.
 
The use of EMA ratings in audiology research is growing. Apps allow researchers to implement the EMA

OBJECTIVES	ENDPOINTS	JUSTIFICATION FOR ENDPOINTS
		
methodology using smartphones in hearing aid outcome research (Wu, Stangl, Zhang, & Bentler, 2015). The EMA approach overcomes several long-standing problems in assessment. First, EMA minimizes the problem of retrospective memory biases in reporting long after specific behaviors or emotional reactions are emitted because respondents can be prompted during real-life situations (Schiffman, Stone, & Hufford, 2008). Users may remember recent events or very emotional events more than others. For hearing aid trials, this also means users may not remember the acoustical background of the situation.
 
Secondly, EMA is representative of real life - surveys are not filled out in an artificial situation during an investigational site visit but rather are possible in many different situations in the life of the subjects. With random sampling (random triggers) it is possible to deduct how often each situation occurs in everyday life, but subjects can also trigger a survey in very important or difficult situations.
 
Thirdly, EMA is context sensitive – subjects may have different needs and preferences in different situations. This can be measured with EMA as the user

OBJECTIVES	ENDPOINTS	JUSTIFICATION FOR ENDPOINTS
		can be asked what situation he/she is in right now. Subjects can for example pay attention to acoustical features, if the questionnaire asks for it.
2. Speech-in-noise recognition performance	
Speech-in-noise recognition performance as measured by the Quick Speech-In-Noise test (QuickSIN)
 
Time point data collected: Cross-over Design: 28 subjects Visit 3
 
Parallel-arm Design: 12 subjects Visit 3 38 subjects Visit 2
	This is an objective measure of Hearing aid benefit with known psychometric properties to be comparable to related SF strategy research.
3. Hearing disability in communication situations	
Hearing disability resulting from hearing loss quantified by the short form of the Speech, Spatial, and Qualities of Hearing Scale for clinical use: the SSQ-12 questionnaire
 
Time point data collected: Cross-over Design: Visit 1, 2, 3
 
Parallel-arm Design: 12 subjects Visit 1, 2, 3 38 subjects Visit 1 and 2
	This is a subjective measure of Hearing aid benefit with known psychometric properties to be comparable to related SF strategy research. The SSQ-12 (Noble, Jensen, Naylor, Bhullar, & Akeroyd, 2013) is selected as a verified tool to provide insights into other components of hearing function.
Secondary Gain Selection		
Individual frequency-specific real-ear gain comparison of the two different fittings (Vibe SF /HCP fit).	
Individual frequency-specific real-ear gain comparison for the two different fitting strategies (Vibe SF/HCP fit) for each ear as measured with probe-mic measures (REM).
 
Time point data collected: Cross-over Design: Visit 3
 
Parallel-arm Design: 12 subjects Visit 3 38 subjects Visit 2
	Objective comparison of real-ear gain (Vibe SF vs. HCP fit) to characterize performance and establish the comparability of the Vibe SF and HCP fit parameters
Secondary Preference		

Fitting (Vibe SF/HCP fit) preference reported by the subject.	
Fitting preference between the Vibe SF or HCP fit strategy.
 
Subjects will be asked to give their response on a 5-point Likert scale to the following question: Based on your listening experiences regarding speech understanding, sound quality and naturalness for both products, if you could keep one pair of these hearing aids, which would you choose?
 
Time point data collected: Cross-over Design: Visit 3
 
Parallel-arm Design: 12 Subjects: Visit 3
	Assessment of perceived hearing aid benefit should include the dimension of fitting preference of the subject.
Secondary Safety Objective		
To estimate the rate of safety when the subject is using the Vibe SF hearing aids.	
The number of adverse device effects (ADEs) in the time period when the subject is using the Vibe SF strategy hearing aids.
 
Time point data collected: Cross-over Design: Visit 1-3, Field Tests 1-2
 
Parallel-arm Design: 12 Subjects: Visit 1-3, Field Test 1-2 38 Subjects: Visit 1 and 2, Field Test 1
	Record, track and report device-related events as part of the risk management process for the SF strategy validation.

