1 PROTOCOL SUMMARY

1.1 SYNOPSIS

Title: Self-Fitting (SF) Strategy Validation NSR Device Study Protocol: **SF Study**

Study Description: A prospective, randomized controlled, adaptive design, non-inferiority, pre-market and NSR device study. To be conducted in a minimum of 28 adult subjects with mild-to-moderate hearing loss to validate the effectiveness of the *Vibe SF* strategy. Validation measures subject's perceived hearing aid benefit when using the *Vibe SF* self-fit hearing aids and when using Silk 1X Hearing Care Professional (HCP) fit hearing aids.

The study begins with a cross-over design. At the interim analysis, the possibility of an interaction effect is evaluated through a nuisance parameter. If it is determined to be likely, the design is switched to a parallel-group design with a larger sample size. Only data from the first period will be included from those subjects who early on participated in the cross-over design.

The Silk 1X HCP fit hearing aids are fitted to National Acoustic Laboratories Nonlinear Version 2 (NAL-NL2) prescriptive targets, verified by probe-mic real-ear measures (REM). The null hypothesis (H_0) is that subject's perceived hearing aids benefit using *Vibe SF* hearing aids is inferior to Silk 1X HCP fit hearing aids, and the alternative hypothesis (H_a) is that subject's perceived hearing aids benefit using *Vibe SF* hearing aids is non-inferior to that using Silk 1X HCP fit hearing aids.

Description of Study**Intervention:**

The mechanism for validating the *Vibe SF* strategy will be to compare subject's perceived hearing aid benefit after two 14 days series of using *Vibe SF*/Silk 1X HCP fit hearing aids.

Objectives:**Primary Effectiveness Objective:**

To demonstrate that the *Vibe SF* strategy is non-inferior to the HCP fit strategy in subject's perceived hearing aid benefit after using the *Vibe SF* and Silk 1X HCP fit hearing aids in real-life conditions.

Secondary Hearing Aid Benefit Objectives:

To score each of the following hearing aid benefit performance measures when the subject is using the *Vibe SF* and Silk 1X HCP fit hearing aids:

1. Sound quality, speech understanding and hearing aid satisfaction real-time assessment,
2. Speech-in-noise recognition performance, and
3. Hearing disability in communication situations.

Secondary Gain Selection Objective:

Individual frequency-specific real-ear gain comparison of the two different fitting strategies (*Vibe SF* and HCP fit).

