8.1.1 SCREENING

Potential subjects will be recruited locally by outreach at the investigator sites, local advertisements, social media advertisements and professional recruiting service. Initial phone/electronic screening will include the question of whether he/she has trouble hearing in noise. If no, they will be excluded. Those remaining will then be asked to rate on a scale of 1-4 her/his perceived hearing loss (no trouble, a little trouble, a lot of trouble, and cannot hear). Listeners at the two extremes will be excluded.

Listeners with appropriate responses are provided an overview of the study intent (subject information) and invited into the clinic to be assessed for eligibility, according to inclusion and exclusion criteria, as described in Section 5.1 and 5.2.

The session begins with otoscopy, tympanometry and a standard audiometric evaluation consisting of air and bone conduction thresholds for each ear. If it is determined they have mild-to-moderate hearing impairment and fulfil all inclusion criteria they will be given study subject information and asked for their voluntary informed consent to participate in the clinical study.

If at this time a subject is identified with significant asymmetries in hearing, the HCP will refer them to an audiologist and/or ENT for follow-up and subject will be excluded from the study (screen failure).

8.1.2 VISIT 1

Subjects complete two questionnaires concerning unaided hearing¹: the APHAB and SSQ-12. The subjects can ask questions, and the HCP or assistant reads through the filled-out questionnaires with the subject to make sure everything is understood and filled out appropriately.

¹ Participants that have experience with hearing aids are nonetheless asked to fill out the questionnaires as they would *without* the use of their hearing aids in order to have the same baseline for all participants.

Investigational staff complete the randomization process to determine which pair of study hearing aids the subject will receive.

Hearing aid fitting is conducted in a quiet dedicated hearing aid fitting and counselling room.

The subjects starting with the *Vibe SF* strategy, independently fit their *Vibe SF* hearing aids bilaterally themselves using the *EasyFit* web application on the study smartphone provided to them. They are provided with *Vibe SF* Safety and Maintenance Information, Quick-Start Guide and a Quick-Start Card. The HCP will not interfere or assist subject in fitting their hearing aids.

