3. Speech understanding,
4. Satisfaction

If the timing is inconvenient (e.g., driving a car), the subject can delay the response to the survey (reminder is given to not delay the response unduly, e.g., for more than 1 hour).

Phone calls (approximately after 3 days +3 days field testing) are scheduled with investigational staff. These calls are intended to ensure that all EMA data collection tools are functioning and subjects are reminded to report any adverse device effects (ADE) occurring during field use. The subject also has the possibility to call/e-mail the investigation staff when needed; however, to mitigate the potential for introducing bias through counselling of the self-fit group, any questions about the *Vibe SF* fitting strategy or how to use the device will not be answered by the investigational staff.

For the subjects who start in the HCP fit strategy group, based on complaints the subjects have about sound quality, the audiologist/HCP is able to invite the subject for an in-person fine-tuning visit and adjust the fitting on their *Silk 1X* as in a real-life HCP fitting (standard clinical care).

Subjects are asked to report any ADEs occurring during field use.

All communication with the HCP and/or investigation staff during the field tests will be documented and saved.

8.1.4 VISIT 2

Subjects return to the clinic after approximately two weeks Field Test 1 use. Subjects complete two questionnaires: the APHAB and the SSQ-12, to reflect their hearing experience aided with the Field Test 1 hearing aids. An HCP or assistant reads through the filled-out questionnaires with the subject to make sure everything is understood and filled out sufficiently.

Subjects are asked to report any ADEs occurring during field use.

Cross-over design:

The Field Test 1 HCP fit strategy subjects now cross over to the *Vibe SF* strategy group. Subjects independently fit their *Vibe SF* hearing aids bilaterally themselves using the *EasyFit* web application on the study smartphone. They are provided with the *Vibe SF* Safety and Maintenance Information, Quick-Start Guide and Quick-Start Card (see Appendix II). The HCP will not interfere or assist the subject with the self-fitting.

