8.1.7 VISIT 3 (ONLY FOR CROSS-OVER DESIGN)

At the final session after approximately 4 weeks of total field use with a 5-day washout period after two weeks of field use, each subject returns the hearing aids from their second field use test.

Subjects are asked to report any ADEs occurring during field use.

Subjects again complete two questionnaires: the APHAB and the SSQ-12, reflecting their hearing experience aided with the Field Test 2 hearing aids. An HCP or assistant reads through the filled-out questionnaires with the subject to make sure everything is understood and filled out sufficiently.

Effectiveness is measured with QuickSIN in an unaided condition and aided with the *Vibe SF* and Silk 1X HCP fit hearing aids in a sound attenuated booth. Aided testing will be conducted double-blinded and subject is given their field test 1 and 2 devices (*Vibe SF* and Silk 1X HCP fit hearing aids) in randomized order.

REM will be conducted double-blinded, and the subject is given field test 1 and 2 devices (*Vibe SF* & Silk 1X HCP fit hearing aids) in randomized order.

The subject will be asked to fill out a 5-point Likert scale to respond to the prompt: *Based on your listening experiences regarding speech understanding, sound quality and naturalness for both products, if you could keep one pair of these hearing aids, which pair would you choose: Greatly prefer A, Somewhat Prefer A, No Preference, Somewhat Prefer B, Greatly Prefer B.*

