9.4.1.1 DESCRIPTIVE STATISTICS

This section describes the descriptive statistics that will be provided with each analysis. The statistics depend on the type of variable (endpoint) that is analyzed. All secondary objectives involve descriptive analyses only.

Descriptive statistics of subject demographics and baseline hearing status will be tabulated. No comparisons will be made because the same subjects serve as *Vibe SF* strategy and HCP fit strategy subjects in this cross-over study.

The descriptive statistics that will be presented will depend on the data type:

- 1) Continuous data will be summarized using n, mean, SD, minimum and maximum values.
- 2) Categorical data will be summarized using frequency and percentage.
- 3) Time-to-event data will be summarized using percentages at relevant time points, along with effective sample size and the 95% confidence interval.
- 4) Frequency (count) data will be summarized as a categorical variable if there are 5 or fewer values (see #2), or as a continuous variable if there are more than 5 distinct values (see #1).

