9.4.3 ANALYSIS OF THE SECONDARY ENDPOINTS

Descriptive statistics will be reported on each endpoint by fitting strategy and overall, according to the list in Section 9.4.1.1. In addition, some endpoints require more detailed description. Additional descriptive statistics that will be reported are listed with the endpoints.

EMA Scores: Descriptive statistics of the scores will be reported by fitting strategy and measurement time for each real-life condition.

QuickSIN Scores: Descriptive statistics of the scores will be reported by fitting strategy and measurement time.

SSQ-12 Scores: Descriptive statistics of the scores will be reported by fitting strategy and measurement time for each subscale.

Protocol #: D00232675

08 September 2021

Gain Selection: Descriptive statistics of the probe-mic REM will be reported by fitting strategy and measurement time.

Fitting Preference: Descriptive statistics of the scores will be reported by fitting strategy and measurement time.

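### QuickSIN and SSQ-12 are planned as raw-score summaries only, so the SD and interval of the within-subject HCP fit minus SF difference, and of the aided-versus-unaided benefit, cannot be recovered from the tables

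*Combined protocol and SAP*

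**What the plan says.** **Objective and justification.** The Synopsis words the secondary objective as "To score each of the following hearing aid benefit performance measures when the subject is using the" two study devices. Section 3 places QuickSIN and SSQ-12 under Secondary Hearing Aid Benefit. QuickSIN is justified by "This is an objective measure of Hearing aid benefit with known psychometric properties to be comparable to related SF strategy research" and SSQ-12 by "This is a subjective measure of Hearing aid benefit with known psychometric properties to be comparable to related SF strategy research".

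**Data collected, cross-over branch.**
- QuickSIN: all three conditions are run at Visit 3. Section 8.1.7 says "Effectiveness is measured with QuickSIN in an unaided condition and aided with the" two fitted devices, with the aided runs double-blind and in random order.
- SSQ-12: at Visit 1 (Section 8.1.2), "Subjects complete two questionnaires concerning unaided hearing". At Visit 2 (Section 8.1.4) it is completed again "to reflect their hearing experience aided with the Field Test 1 hearing aids", and at Visit 3 for the second device.

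**Data collected, parallel branch.** The 38 later subjects have one device and finish at Visit 2. The first 12 have QuickSIN at Visit 3 only, with both devices.

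**Analysis.** Section 9.4.3, repeating 9.1.2, states: "QuickSIN Scores: Descriptive statistics of the scores will be reported by fitting strategy and measurement time". SSQ-12 has the same wording, per subscale. Section 9.4.1.1 fixes the content: "Continuous data will be summarized using n, mean, SD, minimum and maximum values". A benefit score and an HCP fit minus SF difference are defined for APHAB only. Secondary results carry no hypothesis test and are reported only if all three primary nulls are rejected.

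**The concern.** Section 8.1.3 explains that the cross-over was chosen so that devices could be compared within subjects, and Table 4 justifies running all three QuickSIN conditions at one visit partly so that testing can be double-blind. The plan thus obtains paired, blinded data and then tabulates them as two separate columns.

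The primary endpoint is self-report after field use that Section 6.3 says cannot be blinded. REM at Visit 3 is also blinded, but it measures gain. Aided QuickSIN at Visit 3 is therefore the one blinded measure of how well subjects hear with each device, and a natural companion to a positive primary result in the 510(k) report. Without an interval on the device difference, it does that job less well than the data allow. The layout also does not clearly place the unaided QuickSIN score, because unaided is not a fitting strategy and falls at the same visit as both aided runs.

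**Working it through.** The plan states no precision or sample-size figure for QuickSIN or SSQ-12, so there is none to reproduce. The only sized analysis is the primary one (largest N 23, raised to 24). It reproduces and does not bear on this point.

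**1. What the planned tables determine.** If the same subjects contribute to both strategies, the difference of the two means equals the mean of the paired differences. For SSQ-12 this can fail: the mITT set (Section 9.3) takes anyone with the endpoint, so a subject lost after Visit 2 enters one strategy's mean only. The spread of the difference depends on a correlation that the tables do not show. With a common SD for each aided score:

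SD_diff = SD × √(2(1 − ρ))

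This is 1.41 SD at ρ = 0 and 0.45 SD at ρ = 0.9, from identical printed SDs. The same holds for aided versus unaided scores.

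**2. Illustrative precision, cross-over branch.** Inputs: n = 24 completers (Section 9.2). The correlations are assumptions, and results are in units of the SD of one aided score.

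- Two means read as independent: t(0.975, 46) × √(2/24) = 2.013 × 0.2887 = 0.58 SD.
- Paired: t(0.975, 23) × √(2(1 − ρ)/24), with t = 2.069:

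| Assumed ρ | √(2(1 − ρ)/24) | 95% half-width (SD) |
|---|---|---|
| 0 | 0.2887 | 0.60 |
| 0.5 | 0.2041 | 0.42 |
| 0.7 | 0.1581 | 0.33 |
| 0.9 | 0.0913 | 0.19 |

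Averaging over the two orders costs one more degree of freedom (t(0.975, 22) = 2.074) and changes none of these at two decimals.

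**3. Parallel branch.** The arm means come from different people, so an ordinary interval can be built from the planned SDs: 0.57 SD at 25 per arm and 0.59 SD at 23 per arm. What is missing is adjustment for the unaided score. That multiplies the standard error by about √(1 − r²), which is 0.87, 0.71 and 0.60 at assumed unaided-aided correlations of 0.5, 0.7 and 0.8.

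**4. Whether the unaided score exists in that branch.** For SSQ-12 it does, at Visit 1 for everyone. For QuickSIN the documents disagree. The Schedule of Activities marks unaided QuickSIN at Visit 3 only, and at Visit 2 lists only the Field Test 1 device. Table 4 and Section 8.1.4 include an unaided run at Visit 2 for the 38. The first 12 have no Visit 2 QuickSIN at all, and their Visit 3 scores follow use of both devices, so they do not fit a first-period between-arm comparison. Their paired Visit 3 difference would have a half-width of 0.90, 0.64, 0.49 or 0.28 SD at ρ = 0, 0.5, 0.7 or 0.9.

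**The case against.** The strongest reply is that the objective is only to score each measure under each device, and scores by strategy do that. Where the protocol wants a contrast it says so, for APHAB and for REM gain. Keeping the secondaries descriptive is a stated choice. This stands: a reader might infer that the analysis contradicts its objective, and the documents do not support that. The benefit heading and justification make a benefit summary the sensible one, but its absence is an omission, not a contradiction.

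A reader might also infer that no device difference is estimated at all, or that QuickSIN could say nothing about the primary result. Both go too far. Subtracting means gives the point difference when the same completers contribute, and Section 9.4.8 sends subject listings to regulators, who could compute the paired SD. That does not replace a prespecified estimate in the report.

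Nor do the documents support a fixed loss of precision. The plan publishes no interval, so the 0.58 SD figure is what a reader might work out, not planned output. At correlation 0, the only value the protocol uses (for APHAB sizing), pairing gains nothing.

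Finally, the blinding argument covers aided QuickSIN at Visit 3 only. SSQ-12 is self-report after unblinded use, and no double-blinding is described for QuickSIN at Visit 2.

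**Conclusion.** The point holds as a free improvement to the analysis text. In the cross-over branch the planned tables cannot give the SD or interval of the paired device difference or of the benefit, although the data for both are collected. In the parallel branch an interval for the arm difference is available, and the loss is only the efficiency and balance that adjustment for the unaided score would bring. The size depends on correlations that the documents do not give: from no gain at 0 to a half-width of 0.19 SD against 0.58 SD at 0.9, with 24 completers. The primary conclusion, sample size and error control are unaffected.

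**What to change.** In Section 9.4.3, mirrored in 9.1.2, keep the secondaries descriptive with no test and no alpha, and add:

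- **(a) Benefit.** For QuickSIN and each SSQ-12 subscale, the aided-versus-unaided benefit per subject and strategy, with mean, SD and 95% CI. State the sign convention for each measure.
- **(b) Cross-over branch.** The within-subject HCP fit minus SF difference, averaged over the two orders, with mean, SD and two-sided 95% CI.
- **(c) Parallel branch, SSQ-12.** The Visit 2 between-arm difference adjusted for the Visit 1 unaided score, with 95% CI.
- **(d) Parallel branch, QuickSIN.** The same adjusted difference in the 38 single-device subjects only, once the Schedule of Activities is reconciled with Table 4 and Section 8.1.4 on unaided QuickSIN at Visit 2. Report the first 12 subjects' paired Visit 3 difference separately. Because enrolment is not suspended during the interim analysis, also say where any further subject who has already crossed over belongs.

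The cost is SAP wording and a few output tables, settled before results are seen. Items (a) to (c) need no new data, visits or subjects, except that QuickSIN benefit in the 38 under (a), like (d), depends on unaided QuickSIN actually being taken at Visit 2.
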